### 7.5.3 Sensitivity Analysis

- **Multiple imputation assuming missing not at random (MNAR)**

Sensitivity analysis will be performed for secondary efficacy endpoints including change and percent change from baseline in FVC (L) and percent predicted FVC (%), change from baseline in DLco corrected for hemoglobin and DLco not corrected for hemoglobin, and change and percent change from baseline in quantitative HRCT variables using multiple imputations with missing data imputed prior to fitting the linear regression. An assumption of MNAR will be made based upon an approach using regression based multiple imputations with missing data for all subjects imputed from a regression model estimated from patients in the placebo arm who stay on until visit 14. SAS PROC MI and MIANALYZE will be used to generate 100 complete datasets and combine the results from each complete dataset analyzed using ANCOVA model with baseline value, treatment arm, and standard of care as covariates.

- **Excluding subjects with deviations**

All the secondary efficacy analysis described in section 7.5.2 will be repeated using the PP population.

### 7.5.4 Subgroup Analysis

Subgroup analysis will be conducted comparing both active treatment arms with placebo arm to assess consistency of treatment effects across potential prognostic factors.

The following subgroups of ITT population will be analyzed for the secondary efficacy endpoints:

- Standard of care (none vs. nintedanib vs. pirfenidone)
- Anti-fibrosis (none vs. nintedanib or pirfenidone)

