### 2.3 Sample Size and Power

Approximately 120 subjects will be enrolled into the study, with approximately 40 subjects in each of 3 arms. The study will include approximately 35-40 sites, and will enroll approximately 3 to 5 subjects per site.

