## Statistical Analysis Plan

Sponsor Name: Nitto Denko Corporation  
Sponsor Protocol ID: ND-L02-s0201-005

Principle	Value
Display to two more decimal places than collected value	Standard Deviation Confidence interval
Display to p-value	P-values will be rounded to 3 decimal places. P-values less than 0.0005 (e.g. 0.0002) will not be rounded to 3 decimal places (e.g. 0.000) but instead be displayed as <0.001.
Date Format	DDMMYYYY
Statistical Analysis	All statistical tests will be conducted at the 2-sided, 0.05 level of significance. There will be no adjustment for multiplicity.

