## Statistical Analysis Plan

Sponsor Name: Nitto Denko Corporation  
Sponsor Protocol ID: ND-L02-s0201-005

- BMI (<30 vs. ≥30)
- GAP IPF Stage (I vs. II vs. III)
- Duration of IPF since diagnosis to start of study treatment (≤1 vs. 1<-2 vs. 2<-3 vs. 3<-4 vs. ≥4 year)
- Subjects who adhere to the protocol schedule vs. subjects who missed at least one treatment but continued treatment after the interruption vs. early terminated subjects (subjects did not miss any treatment before early termination)
- COVID-19 vaccination (not vaccinated vs. vaccinated prior to treatment start vs. vaccinated while on treatment)

More subgroup analysis may be done ad-hoc given feasible data support.

No adjustment to the significance level for testing will be made. For each subgroup level, the analysis will be as described in 7.5.2 except for subgroup analysis of standard of care, the standard of care covariate will be removed from the analysis model.

If there are less than 10 subjects across both treatment arms in comparison in a subcategory then only descriptive summaries will be provided.

Forest plots will be provided for the secondary efficacy analysis. For rate of decline in FVC (L) or FVC (%FVC) from baseline to Visit 14, the estimated mean slope difference and 95% CI will be summarized and presented on the forest plot for each subgroup category as well as the overall ITT population. For change from baseline in FVC (L), percent predicted FVC (%FVC), DLco corrected for hemoglobin, DLco not corrected for hemoglobin, and quantitative HRCT variables (as described in 3.4.3), estimated means difference and 95% CI will be summarized and presented on the forest plot for each subgroup category as well as the overall ITT population. If the model does not converge then only descriptive summaries will be presented.

For time to event analysis described in section 7.5.2.4 and 7.5.2.5, for each subgroup level of a factor, the hazard ratio (HR) and 95% CI will be calculated from a Cox proportional hazards model that includes treatment and presented on a forest plot. If there are too few events available for a meaningful analysis of a particular subgroup (less than 10 events across both treatment arms in comparison in a subcategory), the HR and 95% CI will not be created for the subgroup and only descriptive summaries (number of event and proportion of subjects with events) will be provided.

[REDACTED]

[REDACTED]

[REDACTED]

[REDACTED]

[REDACTED]

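### SAP 7.5.4 aims to assess consistency of effect across subgroups, but its readable text has no treatment-by-subgroup interaction or heterogeneity measure, and within-level tests at 0.05 do not answer that question

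*SAP*

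**What the plan says.** The aim in SAP 7.5.4 is consistency: "Subgroup analysis will be conducted comparing both active treatment arms with placebo arm to assess consistency of treatment effects across potential prognostic factors". The method is: "No adjustment to the significance level for testing will be made. For each subgroup level, the analysis will be as described in 7.5.2", except that the standard-of-care covariate is dropped when standard of care is itself the subgroup factor. SAP 7.1 adds: "All statistical tests will be conducted at the 2-sided, 0.05 level of significance".

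The Section 7.5.2 analyses carried into each level produce p-values: slope differences for FVC and QLF, a Kruskal-Wallis test for overall change in ILD, and stratified log-rank tests for the time-to-event endpoints.

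The subgroup outputs that 7.5.4 names are estimates. Slope or mean differences with 95% CIs go on a forest plot next to the overall ITT result. Hazard ratios with 95% CIs come from a Cox model within each level, with treatment the only term mentioned.

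Three rules make a level descriptive only. One is by size: "If there are less than 10 subjects across both treatment arms in comparison in a subcategory then only descriptive summaries will be provided". The others are non-convergence of the model and, for time-to-event endpoints, fewer than 10 events across the two arms compared.

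Seven factors are listed: standard of care (3 levels), anti-fibrosis (2), BMI (2), GAP stage (3), duration of IPF (5), adherence to the schedule (3) and COVID-19 vaccination (3).

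**The concern.** Consistency is a question about the difference between subgroup effects. A test inside one level asks whether the effect in that level differs from zero, which is another question. Its answer depends heavily on how many subjects the level holds. A result that is significant in one level and not in its neighbour is therefore weak evidence that the two effects differ.

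The readable text of 7.5.4 has no interaction term, no heterogeneity statistic and no statement of what would count as consistent. A reader of the report would receive many level-specific p-values and no quantity that addresses the stated aim. What is at stake is interpretation: chance differences between levels, for example by background antifibrotic, could be taken as differences in treatment effect.

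**Working it through.** **The plan's own figure.** SAP 2.3 gives about 120 subjects, "with approximately 40 subjects in each of 3 arms", and 3 × 40 = 120 agrees. Neither SAP 2.3 nor Protocol 13.3 states a power, effect size or SD, so overall power below is an assumption and is shown over a range.

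**Number of comparisons.** Listed levels: 3 + 2 + 2 + 3 + 5 + 3 + 3 = 21. The untreated group under standard of care and the untreated group under anti-fibrosis are the same subjects, so 21 − 1 = 20 levels are distinct. With two active arms against placebo that is 20 × 2 = 40 comparisons per endpoint. This is a ceiling, because the descriptive-only rules will remove some.

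**How often a uniform effect looks mixed.** Suppose the effect is identical in all k levels and the levels are of equal size.

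- Expected z for the whole active-versus-placebo comparison: θ = 1.960 + z(power). This is 1.960 at 50% power and 1.960 + 0.842 = 2.802 at 80%.
- Expected z within a level: m = θ/√k.
- Power within a level (two-sided 0.05): p = 1 − Φ(1.960 − m) + Φ(−1.960 − m).
- Chance that some levels are significant and others are not: 1 − p^k − (1 − p)^k.

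| Assumed overall power | Levels | p per level | Mixed pattern | All levels significant |
|---|---|---|---|---|
| 50% | 2 | 0.283 | 0.406 | 0.080 |
| 50% | 3 | 0.205 | 0.488 | 0.009 |
| 50% | 5 | 0.142 | 0.534 | <0.001 |
| 80% | 2 | 0.508 | 0.500 | 0.259 |
| 80% | 3 | 0.366 | 0.696 | 0.049 |
| 80% | 5 | 0.240 | 0.746 | 0.001 |

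Worked line (80%, two levels): m = 2.802/1.414 = 1.981, p = 0.508, mixed = 1 − 0.508² − 0.492² = 0.500.

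**Sensitivity.**
- At 90% overall power the mixed rates are 0.466, 0.746 and 0.835 for 2, 3 and 5 levels.
- With no effect at all they are 0.095, 0.143 and 0.226.
- Unequal levels at 80% power: a 75/25 split gives 0.576, and 50/30/20 gives 0.711.
- A simulation of 20,000 trials at about 80% power, with t-tests within levels, gave 50%, 67% and 71%. The normal approximation is slightly high for small levels.

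**Interaction test.** In the same simulation an F test of treatment-by-subgroup at 0.05 flagged the uniform effect in 5.2%, 5.1% and 4.9% of trials.

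**Smallest level that may be modelled.** At 80% power for 40 vs 40, the standardised difference is 2.802 × √(2/40) = 0.626. With 5 vs 5 (10 subjects across two arms), the expected z is 0.626 × √(5/2) = 0.990, so power is about 17%.

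**Power of the interaction test itself.** With two equal levels, each level effect has twice the variance of the overall effect, so their difference has four times that variance. If the two effects differ by as much as the overall effect, the expected z is 2.802/2 = 1.401. Power is then about 1 − Φ(1.960 − 1.401) = 0.288, or 29%, where the main comparison has 80%.

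**The case against.** The strongest reply is that the SAP never says consistency will be decided by significance within levels. Its named subgroup outputs are estimates with CIs on forest plots, and comparing these by eye, with each other and with the overall result, is an ordinary way to look at consistency. That stands. The mixed-pattern rates describe one possible misreading of the output, not a rule in the plan. The reply is incomplete, though. The Section 7.5.2 analyses bring p-values into each level, and 7.5.4 itself refers to testing: "No adjustment to the significance level for testing will be made". The overall ITT result is promised on the plot only for the continuous endpoints. Point estimates alone can also mislead: at 80% power and five equal levels, at least one level points the wrong way in about 43% of trials under a uniform effect.

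Other points also stand in part.
- Some of 7.5.2.1 and the lines after the time-to-event paragraph of 7.5.4 are blacked out, so an interaction analysis there cannot be excluded. The readable sentence on method nevertheless prescribes an analysis for each level.
- The descriptive-only rules, and the simpler covariance fallback in the QLF model, limit how many fragile fits are reported.
- All these endpoints are secondary, and SAP 7.5.1 names no primary efficacy endpoint. The effect is on interpretation, not on a confirmatory claim.
- An interaction test has low power here, and a non-significant result could itself be misread. That is a reason to report the estimate and its CI, not a reason to leave it out.

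**Conclusion.** The point holds in a limited form. On the readable text, SAP 7.5.4 sets out to assess consistency but provides no measure of how effects differ between levels. The unadjusted p-values within levels do not supply one. Read as significant versus not, they would make a uniform effect look mixed in about 41–50% of trials (two levels), 49–70% (three) or 53–75% (five), against about 5% for an interaction test. Those rates rest on equal levels, a normal approximation and an assumed overall power of 50–80%. They fall to 10–23% if there is no effect.

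Two stronger readings are not supported. A reader might infer that the SAP judges consistency by significance in each level, but it states no such rule and its named outputs are estimates with CIs. A reader might also infer that these subgroups will decide the population of a later trial, but neither document says so. This is a worthwhile and cheap improvement to secondary analyses, not a flaw in the trial's main conclusions.

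**What to change.** For each true baseline factor, add to 7.5.4 one model fitted to the whole ITT population:

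- mean changes: a treatment-by-subgroup term;
- slopes: a treatment-by-time-by-subgroup term;
- time-to-event endpoints: a treatment-by-subgroup term in the Cox model.

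Report the interaction estimate with its 95% CI and p-value beside the forest plot. Keep the level-specific estimates and CIs, label them descriptive, and omit p-values within levels. The level-specific models need not be replaced by a pooled one, which would add a common-variance assumption.

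Limit the interaction models to factors fixed before treatment. Adherence to the schedule and vaccination while on treatment arise after randomisation, so those results should stay descriptive.

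The cost is SAP wording and one extra model per factor and endpoint, with no new data. The downsides are low power at about 40 per arm and sparse levels, such as the five duration bands, that may need collapsing. Any collapsing rule should be fixed before unblinding. The SAP should state beside the plot that a non-significant interaction does not establish consistency.

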## Statistical Analysis Plan

Sponsor Name: Nitto Denko Corporation  
Sponsor Protocol ID: ND-L02-s0201-005

- BMI (<30 vs. ≥30)
- GAP IPF Stage (I vs. II vs. III)
- Duration of IPF since diagnosis to start of study treatment (≤1 vs. 1<-2 vs. 2<-3 vs. 3<-4 vs. ≥4 year)
- Subjects who adhere to the protocol schedule vs. subjects who missed at least one treatment but continued treatment after the interruption vs. early terminated subjects (subjects did not miss any treatment before early termination)
- COVID-19 vaccination (not vaccinated vs. vaccinated prior to treatment start vs. vaccinated while on treatment)

More subgroup analysis may be done ad-hoc given feasible data support.

No adjustment to the significance level for testing will be made. For each subgroup level, the analysis will be as described in 7.5.2 except for subgroup analysis of standard of care, the standard of care covariate will be removed from the analysis model.

If there are less than 10 subjects across both treatment arms in comparison in a subcategory then only descriptive summaries will be provided.

Forest plots will be provided for the secondary efficacy analysis. For rate of decline in FVC (L) or FVC (%FVC) from baseline to Visit 14, the estimated mean slope difference and 95% CI will be summarized and presented on the forest plot for each subgroup category as well as the overall ITT population. For change from baseline in FVC (L), percent predicted FVC (%FVC), DLco corrected for hemoglobin, DLco not corrected for hemoglobin, and quantitative HRCT variables (as described in 3.4.3), estimated means difference and 95% CI will be summarized and presented on the forest plot for each subgroup category as well as the overall ITT population. If the model does not converge then only descriptive summaries will be presented.

For time to event analysis described in section 7.5.2.4 and 7.5.2.5, for each subgroup level of a factor, the hazard ratio (HR) and 95% CI will be calculated from a Cox proportional hazards model that includes treatment and presented on a forest plot. If there are too few events available for a meaningful analysis of a particular subgroup (less than 10 events across both treatment arms in comparison in a subcategory), the HR and 95% CI will not be created for the subgroup and only descriptive summaries (number of event and proportion of subjects with events) will be provided.

[REDACTED]

[REDACTED]

[REDACTED]

[REDACTED]

[REDACTED]

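### Adherence pattern and vaccination during treatment are decided after randomisation, so the active-versus-placebo estimates within these subgroup levels are not randomised comparisons

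*SAP*

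**What the plan says.** SAP 7.5.4 gives the purpose of the subgroup analyses as "to assess consistency of treatment effects across potential prognostic factors", comparing both active arms with placebo. It adds: "The following subgroups of ITT population will be analyzed for the secondary efficacy endpoints". Seven factors follow. Standard of care, anti-fibrotic use, BMI, GAP stage and IPF duration read as baseline factors. The other two are:

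- Adherence: "Subjects who adhere to the protocol schedule vs. subjects who missed at least one treatment but continued treatment after the interruption", with a third level, "early terminated subjects (subjects did not miss any treatment before early termination".
- Vaccination: "COVID-19 vaccination (not vaccinated vs. vaccinated prior to treatment start vs. vaccinated while on treatment".

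All seven are handled alike: "For each subgroup level, the analysis will be as described in 7.5.2" (apart from dropping the standard-of-care covariate in that factor's own analysis). Slope differences, mean differences and hazard ratios with 95% CIs go on forest plots; the slope and mean-difference plots also carry the overall ITT result. On multiplicity: "No adjustment to the significance level for testing will be made". A level is summarised only descriptively if it has fewer than 10 subjects across the two arms compared or if the model does not converge. Hazard ratios also need at least 10 events.

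The readable text has no caveat for the two factors. Some text after the forest-plot paragraph is redacted, so nothing is claimed about it.

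**The concern.** Randomisation takes place on Day 1 before the first infusion (Protocol 12.2.1.1). Missed doses, early termination and vaccination during treatment all come later. The not-vaccinated level has the same defect, since it depends on nobody in it being vaccinated afterwards.

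For adherence, Protocol 8.4.1 requires treatment to stop for an SAE, a significant AE, a severe laboratory abnormality or intercurrent illness when the Investigator judges that continuing is not in the subject's interest. Tolerability and deterioration therefore help decide who stays adherent, and both can differ by arm. A death during treatment also ends the schedule. For overall survival and the composites with death, level membership is thus partly decided by the outcome.

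If one arm loses more of its sicker subjects, its remaining adherent subjects look better with no drug effect; reverse the imbalance and the sign reverses. On the forest plot, such an estimate would look the same as a genuine baseline subgroup.

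**Working it through.** **Plan's own figure.** 3 × 40 = 120, as stated in SAP 2.3. No power, effect size, SD, stopping rate or subgroup size is given, so everything below except the counts rests on assumptions.

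**Counts.** Levels: 3 + 2 + 2 + 3 + 5 + 3 + 3 = 21, so 42 active-versus-placebo contrasts per endpoint. The two factors supply 6 levels and 12 contrasts. Only vaccinated before treatment start is a baseline level, which leaves 5 levels and 10 contrasts decided after randomisation.

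**Adherent level, no drug effect.** Assume 40 per arm, with 8 active subjects (20%) and 4 placebo subjects (10%) stopping. Those with the worst value of a health variable stop, and that variable has correlation r with the 24-week FVC change. Removing the worst fraction p raises the mean of those who remain by r × φ(z_p)/(1 − p) SD.

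- p = 0.20: 0.280/0.80 = 0.350
- p = 0.10: 0.1755/0.90 = 0.195
- Same selection rule in both arms: r × (0.350 − 0.195) = 0.155r
- Selection on active only, random stopping on placebo: 0.350r

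The error rate is the share of 100,000 simulated null trials (32 versus 36 subjects, two-sided t-test at 0.05) that reject. The t-test stands in for the planned model.

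| Selection | r | Bias (SD) | mL at SD 150/200/250 | Error rate |
|---|---|---|---|---|
| Unrelated to health | 0 | 0 | 0 | 5% |
| Both arms | 0.3 | 0.05 | 7/9/12 | 6% |
| Both arms | 0.6 | 0.09 | 14/19/23 | 8% |
| Both arms | 1.0 | 0.15 | 23/31/39 | 16% |
| Active only | 0.6 | 0.21 | 32/42/53 | 14% |
| Active only | 1.0 | 0.35 | 52/70/87 | 34–35% |

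For example, 0.155 × 0.6 = 0.093, and 0.093 × 200 = 18.6 mL.

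A second null simulation (2,000,000 subjects per arm, r = 0.6, SD 200 mL) used 15% non-adherence on placebo and 30–40% on active. The adherent level favoured active by 14 to 42 mL. Where sicker subjects stopped more selectively on active, the non-adherent level pointed to harm, at −42 mL (30%) and −28 mL (40%). Bias was zero with equal rates and equal dependence on health.

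**Vaccination, no drug or vaccine effect.** Time to event had gamma frailty, the vaccination date was independent of arm, 15% stopped on placebo and 15–50% on active. The active/placebo rate ratio among those vaccinated during treatment was 1.00 with equal stopping and 0.95–1.03 otherwise. Among those vaccinated beforehand it was 0.99–1.00. Between levels, with equal stopping, the placebo-arm rate was 13.8 per 100 patient-years (vaccinated during treatment) against 30.5 (not vaccinated). In this model 10–14% were vaccinated after treatment ended and fit none of the three levels.

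**The 10-event rule.** A level of 40 subjects across two arms followed for 34 weeks expects 40 × 34/52.18 × 0.138 = 3.6 events, with about a 0.4% Poisson chance of reaching 10. At 30.5 per 100 patient-years it expects 7.9.

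**Secondary point, baseline factors.** Five IPF-duration levels at 40/5 = 8 per arm pass the 10-subject rule. With one common effect of 0.5 SD, each level's standard error is √(2/8) = 0.5 SD. The chance that at least one level points the wrong way is 1 − (1 − Φ(−1))⁵ = 58% (42% at 0.63 SD, 70% at 0.4 SD). Separate per-level estimates therefore say little about consistency.

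**The case against.** Much of the opposing case stands.

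- A reader might infer that immortal time invalidates the vaccination hazard ratios between arms. The planned contrast is active versus placebo within a level, and both arms share the wait for vaccination. The distortion falls mainly on comparisons between levels, which the SAP does not plan.
- A reader might also infer that a subject must be free of events to be vaccinated on treatment. The documents do not say so. Stopping after an AE rests on Investigator judgement (Protocol 8.4.1), and Protocol 10.3.2.5 foresees exacerbations being treated during the study. Only death necessarily rules out later vaccination.
- It is tempting to say that nobody who missed a dose and later terminated has a level. Level two takes those who missed, resumed and later stopped. Those who missed and never resumed are the unclear group.
- The 10-subject, 10-event and non-convergence rules will suppress many estimates, including most vaccination hazard ratios at the assumed rates.
- Protocol 18.6.2.2 allows up to two remote visits under COVID-19 restrictions. Doses missed for that reason should not depend on arm, which weakens the bias. The SAP does not limit the level to that cause.
- These are exploratory analyses. The SAP names no primary efficacy endpoint (7.5.1), and the primary objective is safety.

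None of this makes the within-level contrasts randomised, and none of it justifies presenting them unlabelled among baseline factors.

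**Conclusion.** The point holds, led by adherence. The within-level contrasts can show spurious benefit or harm. Under the assumed 20% versus 10% stopping, the adherent-level bias is about 0.09 SD with 8% error at correlation 0.6, and about 0.15 SD with 16% error at 1.0, when both arms select on health. A reader might take 0.35 SD and 35% as the expected size. That needs perfect selection on active and purely random stopping on placebo, and nothing in the documents supports it. The bias vanishes if stopping is unrelated to health, or if rates and selection are equal across arms. For vaccination the between-arm bias is likely small. The ITT efficacy estimates and primary safety results are not affected. This should be changed, but it does not threaten the trial's main conclusions.

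**What to change.** In SAP 7.5.4:

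1. Restrict active-versus-placebo subgroup estimates and forest plots to factors known before the first dose.
2. Recode vaccination as vaccinated before first dose, yes or no. This leaves 15 + 2 = 17 levels and 34 contrasts per endpoint.
3. Show the adherence/early-termination and on-treatment vaccination groups descriptively, labelled as non-randomised.
4. State where to count subjects who missed doses and never resumed, and those vaccinated after treatment ended.
5. As a secondary change, for the baseline factors print the treatment-by-subgroup interaction estimate with its CI beside the level estimates.

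The cost is SAP wording and minor programming, with no new data and no effect on the main analyses. This is a free improvement.
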